11.5 Dose delay/modification

Intrapatient dose reduction will be allowed depending on the type and severity of toxicity encountered provided that criteria for patient withdrawal from study treatment have not been met. The dose levels for sorafenib are as described below:

Starting dose 0	Sorafenib 400 mg twice daily
Dose level -1	Sorafenib 400 mg daily
Dose level -2	Sorafenib 400 mg every other day

If further dose reduction is required, the patient should be taken off-protocol.

Patients who require a treatment delay of >4 consecutive weeks should also be taken offprotocol.

IRB#:09-016A(9)

The following tables describe the recommended dose modifications for sorafenib-associated toxicities, including hand-foot skin reaction (Table 11.5.1), treatment-emergent hypertension (Table 11.5.2), exacerbation of baseline hypertension (Table 11.5.3) and other general hematologic and non-hematologic toxicities (Table 11.5.4).

Grade	Occurrence	Suggested Dose Modification		
Grade 1 Numbness, dysesthesia, paresthesia, tingling, painless swelling, erythema or discomfort of the hands or feet which does not disrupt the patient's normal activities	Any	Promptly institute supportive measures such as topical therapy for symptomatic relief and continues orafenib treatment.		
Grade 2 Painful erythema and swelling of the hands or feet and/or discomfort affecting the patient's	First	 Promptly institute supportive measures such as topical therapy for symptomatic relief and consider a decrease of sorafenib dose to 400 mg daily for a minimum of 7 days and up to 28 days. If toxicity resolves to grade 0-1 after dose reduction, increase sorafenib back to full dose of 400 mg BID. 		
normalactivities		• If toxicity does not resolve to grade 0-1 despite dose reduction, interrupt sorafenib treatment for a minimum of 7 days and until toxicity has resolved to grade 0-1.		
		• When resuming treatment after dose interruption, resume sorafenib at a reduced dose of 400mg daily.		
		• If toxicity is maintained at grade 0-1 at reduced dose for a minimum of 7 days and up to 28 days, increase sorafenib back to full dose of 400 mg BID		
	Second or Third occurrence	As for first occurrence. Upon resuming sorafenib treatment, decrease dose by one dose level (400 mg daily or 400 mg every other day).		
		Decision whether to dose re-escalates hould be based on clinical judgment and patient preference.		
	Fourth occurrence	Decision whether to discontinue sorafenib treatments hould be made based on clinical judgment and patient preference		
Grade 3 Moist desquamation, ulceration, blistering or severe pain of the hands or feet, or severe discomfort that causes the	First occurrence	 Institute supportive measures such as topical therapy for symptomatic relief and interrupt sorafen ib treatment for a minimum of 7 days and until toxicity has resolved to grade 0–1 When resuming treatment after dose interruption, decrease sorafenib by one dose level (400 mg daily or 400 mg every other day) If toxicity is maintained at grade 0-1 at reduced dose for a minimum of 7 days 		
patient to be unable to work or performactivities		and up to 28 days, increase by one dose level (400mg BID or 400 mg daily) As for first occurrence. Upon resuming sorafenib treatment, decrease dose by one		
of daily living	Second occurrence	dose level (400 mg daily or 400 mg every other day).		
		Decision whether to dose re-escalate should be made based on clinical judgment and patient preference.		

Table 11.5.1: Suggested dose modifications for sorafenib for hand-foot skin reaction

IRB#: 09-016A(9)

	Third occurrence	Decision whether to discontinue sorafenib treatment should be made based on clinical judgment and patient preference.
--	------------------	---

Table 11.5.2: Dose Modifications of Sorafenib for Hypertension

Grade	Antihypertensive	Blood Pressure	Sorafenib Dose	
(CTCAE v3.0)	Therapy	Monitoring		
Grade 1	None	Routine	No change	
Grade 2 (asymptomatic)	Initiate monotherapy (suggest dihydropyridine calcium-channel blocker)	Increase frequency and monitor (by health professional) every 2 days until stabilized	No change	
Grade 2 (symptomatic/ persistent) OR Diastolic BP > 110 mm Hg OR Grade 3	Add agent(s): Ca ⁺⁺ channel blocker (if not already used), K+ channel opener (angiotensin blockers), beta-blocker, thiazide diuretic	Increase frequency and monitor (by health professional) every 2 days until stabilized; continue qod monitoring to stabilization after dosing restarted.	Hold* Sorafenib until symptoms resolve and diastolic BP < 100 mm/Hg. Resume treatment at 1 dose level lower**	
Grade 4			Off protocol therapy	
 * Patients requiring a delay of > 21 days should go off protocol therapy unless, in the treating physician's opinion, the patient may benefit from continued treatment ** Patients requiring >2 dose reductions should go off protocol therapy. 				
CTCAE v3.0 definitions Grade 1: asymptomatic, transient (<24 hrs) increase by > 20 mmHg (diastolic) or > 150/100 if previously				
WNL; intervention not indicated Grade 2: recurrent or persistent (>24 hrs) or symptomatic increase by >20 mmHg (diastolic) or to >150/100 if previously WNL; monotherapy may be indicated. Grade 3: requiring more than one drug or more intensive therapy than previously Grade 4: life threatening (a g hypertensive arisis)				

Grade 4: life threatening (*e.g.*, hypertensive crisis)

Table 11.5.3: Suggested dose modifications for sorafenib for exacerbation of hypertension in patients with baseline diagnosis of hypertension.

Amended: 05/12/15

IRB#:09-016A(9)

Hypertension grade	Suggested dose modification		
Grade 1: Asymptomatic, transient (<24 hours)	Increase blood pressure monitoring		
increase by >20 mmHg (diastolic) or to			
>150/100 mmHg if previously within normal			
limits (WNL)			
Grade 2: Recurrent or persistent (\geq 24 hours)	Additional anti-hypertensive therapy per		
increase by >20 mmHg (diastolic) or to	standard management and continue sorafenib		
>150/100 mmHg if previously WNL			
OR			
Grade 3: Requiring >1 drug or more intensive			
therapy than previously			
BUT diastolic blood pressure <110 mmHg			
Grade 2 but symptomatic	1. Hold sorafenib until symptoms resolve and		
OR	diastolic BP <100 mmHg		
Diastolic blood pressure ≥110 mmHg	2. Additional anti-hypertensive therapy.		
	3. Restart sorafenib at one dose level lower.*		
	4. If diastolic BP is ≥ 100 mmHg on anti-		
	hypertensive therapy, decrease by another		
	dose level.		
Grade 4: Life-threatening consequences, e.g.	Discontinue sorafenib; institute supportive		
hypertensive crisis	measures		

*may be able to resume sorafenib at full-dose later if BP is <140/80 on anti-hypertensive therapy.

Table 11.5.4: Dose modifications for sorafenib hematologic and non-hematologic toxicities			
(other than hand-foot reaction and hypertension)			

Toxicity	Grade 1	Grade 2	Grade 3*	Grade 4*
Non-	Continue at the	Continue at the	Withhold dose for at	Withhold dose for

Amended: 05/12/15

IRB PB

IRB#: 09-016A(9)

hamatalagia	same dose level.	same dose level.	loget 7 davis until	at logat 7 days until
hematologic	same dose level.	same dose level.	least 7 days until	at least 7 days until
			toxicity is grade ≤ 1 ,	toxicity is grade
			then resume	≤ 1 , then resume
			treatment at one dose	treatment at one
			level lower.	dose level lower,
				or discontinue at
				the discretion of
				the principal
				investigator after
				discussion with
				study sponsor.
Hematologic	Continue at the	Continue at the	Withhold dose for at	Withhold dose for
	same dose level.	same dose level.	least 7 days until	at last 7 days until
			toxicity is grade <2,	toxicity is grade
			then resume	≤ 2 , then resume
			treatment at one dose	treatment at one
			level lower.	dose level lower,
				or discontinue at
				the discretion of
				the principal
				investigator after
				discussion with
				study sponsor.

*Patients who develop grade 3 fever/chills, grade 3 elevation of hepatic transaminases with ALT and AST <10X ULN, grade 3 hyperlipasemia or hyperamy lasemia without clinical or other evidence of pancreatitis, grade 3 leukopenia, or grade 3/grade 4 lymphopenia may continue study treatment without interruption at the discretion of the investigator.

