11.0 TOXICITIES/SIDE EFFECTS

11.1 General considerations

Subjects must be carefully monitored for adverse events. This monitoring includes clinical laboratory tests. Adverse events should be assessed on a continuous basis, with the highest grade recorded according to National Cancer Institute Common Terminology Criteria for Adverse Events (NCI-CTCAE), version 3.0.⁴⁶ Adverse event should be assessed in terms of seriousness, severity, and relationship to the study drug (See Section 11.6).

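### Table 11.5.3 holds sorafenib for symptoms only at grade 2, so symptomatic grade 3 hypertension with diastolic pressure below 110 mmHg falls in the row that continues dosing

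*Combined protocol and SAP*

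**What the plan says.** Section 11.5 has two hypertension tables. Its introductory text assigns Table 11.5.2 to treatment-emergent hypertension and Table 11.5.3 to exacerbation of hypertension already present at baseline.

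In Table 11.5.3 the second row covers recurrent or persistent grade 2, or grade 3, with one qualifier: "BUT diastolic blood pressure <110 mmHg". The action is additional antihypertensive therapy per "standard management and continue sorafenib". The third row is triggered by "Grade 2 but symptomatic" or by diastolic pressure of 110 mmHg or more. Its action is to hold until symptoms have gone and diastolic pressure is under 100 mmHg, add antihypertensives, and restart one level lower.

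In Table 11.5.2 the hold row reads "Grade 2 (symptomatic/ persistent) OR Diastolic BP > 110 mm Hg OR Grade 3".

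The grade definitions printed under Table 11.5.2 include "recurrent or persistent (>24 hrs) or symptomatic increase by >20 mmHg (diastolic") at grade 2, and "Grade 3: requiring more than one drug or more intensive therapy than previously". Section 11.1 adds: "Adverse events should be assessed on a continuous basis, with the highest grade recorded".

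**The concern.** Table 11.5.3 treats symptoms as a reason to stop dosing: they trigger the hold at grade 2, and the hold lasts until they resolve. At grade 3 the symptom trigger is missing and no reason is given. Two patients with the same pressure and the same symptoms can then be handled in opposite ways, and the one who needs more antihypertensive treatment is the one who keeps taking the drug.

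The case is realistic. Grade 3 is defined by treatment need, so a patient already on an antihypertensive who presents with symptoms and needs more therapy can be graded 3. Such patients are eligible, because Section 6.2 excludes only uncontrolled hypertension. In the phase II renal cell trial described in Section 3.5.2, hypertension was the most common grade 3/4 event, at 31% of patients. That is another tumour type, and the figure does not give the symptomatic share. What is at stake is patient safety; no effect on the primary endpoint or its decision rule is claimed.

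**Working it through.** The plan states no figure on this point, so the check sets the rows side by side.

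**Row check, Table 11.5.3.** Test event: baseline hypertension, grade 3, symptomatic, diastolic pressure 105 mmHg.

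| Row | Trigger | Met? | Action |
|---|---|---|---|
| 1 | Grade 1, asymptomatic and transient | No | More monitoring |
| 2 | Grade 2 (recurrent or persistent) or grade 3, diastolic below 110 | Yes: grade 3, and 105 < 110 | Add antihypertensives, continue |
| 3 | Symptomatic grade 2, or diastolic 110 or more | No: not grade 2, and 105 < 110 | Hold, restart one level lower |
| 4 | Grade 4, life-threatening | No | Discontinue |

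Row 2 is the only match.

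**Comparison of the two tables** for a symptomatic patient at 105 mmHg:

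| | Table 11.5.2 | Table 11.5.3 |
|---|---|---|
| Grade 2 | Hold | Hold |
| Grade 3 | Hold | Continue |

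One of the four cells says continue.

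**Can the event be grade 3 without also being grade 2?** Yes. Take a symptomatic rise from 88 to 105 mmHg that needs a further drug. The rise is 105 − 88 = 17 mmHg, short of the more than 20 mmHg that grade 2 asks for. The other route to grade 2, a rise above 150/100, applies only if pressure was previously within normal limits; I assume that a patient with a baseline diagnosis of hypertension is not so classed. The need for a further drug makes the event grade 3.

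**Other text that might supply the hold.**
- Table 11.5.2 holds for grade 3, but Section 11.5 assigns it to treatment-emergent hypertension. A reader who applied both tables would find them in conflict.
- Table 11.5.4 withholds for grade 3 non-hematologic toxicity, but its title excludes hypertension.
- Section 11.4 says only that permanent discontinuation should be considered for severe or persistent hypertension or hypertensive crisis despite adequate treatment. It sets no symptom-based hold.

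**Dose contrast**, from the dose levels in Section 11.5:
- Starting dose: 400 mg × 2 = 800 mg/day.
- Level −1: 400 mg/day, which is 1 − 400/800 = 50% lower.
- Level −2, "Sorafenib 400 mg every other day": 400/2 = 200 mg/day on average, which is 1 − 200/400 = 50% lower again.

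A patient at the starting dose therefore continues at 800 mg/day, against 0 during a hold and 400 mg/day on restart. At level −1 the contrast is 400 mg/day, against 0 and then 200 mg/day on average.

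**The case against.** The strongest reply is that the rows overlap and leave no gap. A symptomatic diastolic rise of more than 20 mmHg meets the grade 2 definition whatever drugs it then needs, and the hold-row label can be read as an exception to the row above. Section 11.1 governs how events are recorded; it does not say that a hold trigger lapses once a higher grade is assigned. Moreover, the hold row itself calls for additional antihypertensives, which can create the grade 3 criterion in a patient already on treatment. On that view the only workable reading is that symptoms mean hold.

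Part of this stands. Section 11.1 is a recording rule, and applying it to dosing is an inference. A clinician may well read the table in the sensible way, and an event first managed as symptomatic grade 2 is already on hold. But the rows are keyed to a grade, and an event assigned grade 3 is not named in the hold row. The 88 to 105 mmHg example never meets grade 2, so overlap does not rescue it. That the table's own action can move an event to grade 3 is a further reason to correct the label.

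Other limits also stand. The table is headed as suggested, although the introduction to Section 11.5 calls its tables recommended modifications. Section 10 requires weekly blood pressure in cycle 1, and Section 13 ends treatment for unacceptable adverse events. The group is narrow: a rise of more than 20 mmHg from 90 passes 110 and triggers the hold on pressure alone. Grade 3 has no pressure threshold, however, so the window does not close. The reduced dose need not last, since a footnote allows full dose again later if pressure is below 140/80 on therapy.

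**Conclusion.** The concern holds. Read as written, Table 11.5.3 suggests continuing sorafenib through a symptomatic grade 3 event with diastolic pressure below 110 mmHg. The same symptoms at grade 2 would lead to a hold, and so would any grade 3 event under Table 11.5.2. Continuing asymptomatic grade 3 below 110 mmHg is not questioned.

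The conclusion rests on two readings: that the rows apply to the grade assigned, and that Table 11.5.2 does not govern patients with baseline hypertension, as the introduction to Section 11.5 indicates. The number of patients affected is unknown. The advisory heading and the narrow group limit the likely harm, but they do not make the written rule right. The change should be made.

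**What to change.** Change two row labels in Table 11.5.3:

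- Hold row: *Grade 2 or 3 but symptomatic, OR diastolic pressure ≥110 mmHg*.
- Continue row: *Asymptomatic grade 2 or 3, with diastolic pressure <110 mmHg*.

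The hold, added antihypertensives and one-level reduction already in the table then cover symptomatic grade 3.

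The change adds no visits, tests or patients. Its cost is a few more holds and dose reductions among symptomatic patients. Some of these could end protocol treatment under existing Section 11.5 rules: a delay of more than 4 consecutive weeks takes a patient off protocol, and so does the need for a reduction below level −2.

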11.6 Adverse event definitions

11.6.1 Adverse event

An adverse event is any untoward medical occurrence in a subject or clinical investigation subject administered with a pharmaceutical product. The adverse event does not necessarily have to have a causal relationship with this treatment. An adverse event can therefore be any unfavorable and unintended sign (including an abnormal laboratory finding), symptom, or disease temporally associated with the use of an investigational product, whether or not considered related to the medicinal product.

Adverse events associated with the use of a drug in humans, whether or not considered drug related, include the following:

- An adverse event occurring in the course of the use of a drug product in professional practice.
- An adverse event occurring from an overdose whether accidental or intentional.
- An adverse event occurring from drug abuse.
- An adverse event occurring from drug withdrawal.

Amended: 05/12/15

IRB#:09-016A(9)

• An adverse event where there is a reasonable possibility that the event occurred purely as a result of the subject's participation in the study (e.g. adverse event or serious adverse event due to discontinuation of anti-hypertensive drugs during wash-out phase) must also be reported as an adverse event even if it is not related to the investigational product.

11.6.2 Serious adverse event (SAE)

A serious adverse event (SAE) is any untoward medical occurrence that at any dose:

- Results in death.
- Is life-threatening.
- Requires in-patient hospitalization or prolongation of existing hospitalization.
- Results in persistent or significant disability or incapacity.
- Is a congenital anomaly or birth defect.
- Is an important medical event.

11.6.3 Adverse event documentation

All adverse events occurring after the subject has signed the informed consent must be fully recorded in the subject's case record form.

Documentation must be supported by an entry in the subject's file. A laboratory test abnormality considered clinically relevant, e.g., causing the subject to withdraw from the study, requiring treatment or causing apparent clinical manifestations, or judged relevant by the investigator, should be reported as an adverse event. Each event should be described in detail along with start and stop dates, severity, relationship to investigational product, action taken and outcome.

11.7 Reporting of serious adverse events (SAE)

Each serious adverse event must be followed up until resolution or stabilization, by submission of updated reports to the designated person. An isolated laboratory abnormality that is assigned grade 4, according to CTC definition, is not reportable as an SAE, unless the investigator assesses that the event meets standard ICH criteria for an SAE. CTC grade 4 baseline laboratory abnormalities that are part of the disease profile should not be reported as an SAE, specifically when they are allowed or not excluded by the protocol inclusion/exclusion criteria.

When required, and according to local law and regulations, serious adverse events must be reported to the Ethics Committee and Regulatory Authorities.

Serious adverse drug-related events should be reported to Bayer/Onyx. In the event of such an event, the investigator should refer to the Pharmacovigilance section of the contract for reporting procedures.

IRB#:09-016A(9)

In brief, the Investigator/Sponsor may report serious adverse drug reactions (SADRs) using a Clinical Research Database (CRDB) Adverse Event report.

All reports shall be sent electronically to:

Electronic Mailbox:	[contact]
[contact]
Address: Mail only	Global Pharmacovigilance - USA Bayer HealthCare Pharmaceuticals Inc. [name]
Address: FDX or UPS only	[name]

Reports for all Bayer products can also be phoned in to the Clinical Communications Department:

[contact]

12.0 CRITERIA FOR THERAPEUTIC RESPONSE/OUTCOME ASSESSMENT

12.1 Measurement of effect

For the purposes of this study, patients should be re-evaluated after the first cycle, i.e. four weeks, of treatment and then every two cycles or eight weeks thereafter. Confirmatory scans should also be obtained no less than four weeks following initial documentation of objective response.

12.2 Definitions

Response and progression will be evaluated in this study using standard Response Evaluation Criteria in Solid Tumors (RECIST) criteria.⁴⁵ Changes in only the largest diameter (unidimensional measurement) of the tumor lesions are used in the RECIST criteria. Note: Lesions are either measurable or non-measurable using the criteria provided below. The term "evaluable" in reference to measurability will not be used because it does not provide additional meaning or accuracy.

12.2.1 Measurable disease

Measurable lesions are defined as those that can be accurately measured in at least one dimension (longest diameter to be recorded) as ≥ 20 mm with conventional X-rays or ≥ 10 mm

Amended: 05/12/15

IRB#: 09-016A(9)

with CT or MRI scan. All tumor measurements must be recorded in millimeters (or decimal fractions of centimeters).

Tumor lesions within a prior radiation field are considered measurable as long as disease progression has been documented in these lesions after prior radiotherapy.

12.2.2 Non-measurable disease

All other lesions (or sites of disease), including small lesions (longest diameter <20 mm using X-ray or <10 mm using CT or MRI scan), are considered non-measurable disease. Bone lesions, leptomeningeal disease, ascites, pleural/pericardial effusions, lymphangitis cutis/pulmonis, inflammatory breast disease, abdominal masses (not followed by CT or MRI), and cystic lesions are all non-measurable.

12.2.3 Target lesions

All measurable lesions up to a maximum of five lesions per organ and 10 lesions in total, representative of all involved organs, should be identified as target lesions and recorded and measured at baseline. Target lesions should be selected on the basis of their size (lesions with the longest diameter) and their suitability for accurate repeated measurements (either by imaging techniques or clinically). A sum of the longest diameter (LD) for all target lesions will be calculated and reported as the baseline sum LD. The baseline sum LD will be used as reference by which to characterize the objective tumor response.

12.2.4 Non-target lesions

All other lesions (or sites of disease) should be identified as non-target lesions and should also be recorded at baseline. Non-target lesions include measurable lesions that exceed the maximum numbers per organ or total of all involved organs as well as non-measurable lesions. Measurements of these lesions are not required but the presence or absence of each should be noted throughout follow-up.

12.3 Guidelines for evaluation of measurable disease

All measurements should be taken and recorded in metric notation using a ruler or calipers. All baseline evaluations should be performed within four weeks before the beginning of the treatment.

The same method of assessment and the same technique should be used to characterize each identified and reported lesion at baseline and during follow-up. Imaging-based evaluation is preferred to evaluation by clinical examination when both methods have been used to assess the antitumor effect of a treatment.

Clinical lesions. Clinical lesions are not considered measurable. Amended: 05/12/15

- 37 -

IRB#:09-016A(9)

Chest X-ray. Lesions on chest x-ray are acceptable as measurable lesions when they are clearly defined and surrounded by aerated lung. However, CT is preferable.

Conventional CT and MRI. These techniques should be performed with cuts of ≤ 10 mm in slice thickness contiguously. Spiral CT should be performed using a 5 mm contiguous reconstruction algorithm. This applies to tumors of the chest, abdomen, and pelvis. Head and neck tumors and those of extremities usually require specific protocols.

Ultrasound (U/S). U/S should not be used to measure tumor lesions. It is, however, a possible alternative to clinical measurements of superficial palpable lymph nodes, subcutaneous lesions and thyroid nodules. U/S might also be useful to confirm the complete disappearance of superficial lesions usually assessed by clinical examination.

Endoscopy/laparoscopy. The utilization of these techniques for objective tumor evaluation has not yet been fully and widely validated. Their uses in this specific context require sophisticated equipment and a high level of expertise. Therefore, the utilization of such techniques for objective tumor response is not permitted. However, such techniques can be useful to confirm pathological complete response when biopsies are obtained.

Tumor markers. There are no validated tumor markers for the assessment of esophageal and GE junction cancers. As such, they cannot be used to assess response.

